Disease-induced fatigue that is manifested by physical or mental illness and / or is a consequence of treatments and medications is a common topic of research in disease management. Such fatigue can be managed by addressing medically treatable causes (15). However, many older people experience general fatigue with no specific known cause. This type of fatigue has been reported in 27-53% of community- dwelling older people worldwide (16). General fatigue is partly caused by age-related bio- physiological changes, such as reduced muscle strength and mass, leading to decreased muscle endurance. This, together with a gradual decline in cardiovascular and pulmonary functions also leads to a reduction in the maximal heart volume and to a decrease in the vital capacity and expiratory volume of older people. These changes predispose older people to reduce their rate of oxygen consumption during activities, and cause them to feel more fatigue when performing even mild daily activities (1). The general fatigue experienced by older people has been likened to a continuum between mild ‘tiredness’ and severe ‘exhaustion’ (17). Exhaustion (a severe level of fatigue) may not be relieved by rest, leading to a decreased capacity for everyday physical and mental activities (17). The terms ‘exhaustion’ and ‘fatigue’ are used interchangeably in most studies, and also in this proposal. Longitudinal studies have shown that older people with self-reported general fatigue have more restricted activities(3), poorer physical function, slower gait speed, and disability(4, 5), increased utilization of home-help and hospital services(6), and even a higher risk of mortality in the long term (i.e., 3-5 years)(18). In fact, exhaustion, together with unintentional weight loss, low levels of activity, a slow walking speed, and a decreased grip strength are the five phenotypes of frailty(7). This physiological state of increased vulnerability to stressors results from a decrease and possible dysregulation of reserves in multiple physiological / biologic systems (8, 19-21). Epidemiological studies have found that exhaustion is one of the most common characteristics exhibited in older people with frailty. A longitudinal study of 420 non-frail older women found that women with exhaustion were 3-5 times more likely to develop frailty seven years later (at which 80% of them developed frailty) when compared with those without exhaustion(2). The empirical evidence shows that general fatigue is prevalent among older people and can predict frailty and disability in the long term. This evidence raises the concern that a decrease in the production of energy or an inability to cope with an increased utilization of energy could be very much a part of the transition to a final common pathway of frailty and disability. Despite this, the management of fatigue has not yet received adequate attention in gerontological care (12).

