Participants will be assessed on a variety of outcomes (described below) at week 8 (T1 at mid-term programme), 1 week (T2 immediate effect), 6 and 12 months after the programme (T3 and T4), which will be compared with the baseline assessment (T0). All assessments will be carried out by a part-time RA, regarded as an independent assessor, who will be blinded to the group assignments.

Socio-demographic data: The following data will be collected: 1) age, gender, marital status,

exercise habits, living conditions, and level of education, 2) the participants' health-related information, including cognitive status and medications. Additionally, their levels of comorbidity will be assessed using the Chinese version of the Charlson comorbidity index (C-CCI). The C-CCI score is the sum of the comorbidity and age scores, in which scores of 0, 1-2, 3-4, and > 5 represent the comorbidity level as none, low, medium, and high, respectively⁵⁰. The health services utilization of the parents in the past 12 months and during the study period, such as the number, duration, and causes of hospital admissions and scheduled/non-scheduled clinical visits, will be collected during each measurement time point and will be treated as a co-variate if needed.

Primary outcome measurement: Fatigue will be assessed using the 20-item Chinese Multidimensional Fatigue Inventory (CMFI-20)⁽⁵¹⁾. This scale was validated among 385 local cancer patients. A factor analysis revealed that it contains three factors (namely, physical, mental, and spiritual) with a factor loading ranging from 0.52 to 0.75. The Cronbach's α was between 0.7 and 0.8 for three domains and the total of the CMFI-20 score. It supports the view that the CMFI-20 is a reliable and valid instrument.

Secondary outcome measurements

Physical Endurance will be evaluated using different physical tests. First, the participants' lower-limb and upper-limb strength will be assessed using a 30-second chair stand test⁽⁵²⁾ and a handheld Jamar Hydraulic Hand Dynamometer⁽⁵³⁾, respectively. Their mobility and overall physical endurance will be assessed through the TUG test and by their gait speed (6-m walk).

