Procedures: (*Appendix IV*: Detailed Ethical Considerations; *Appendix V*: CONSORT diagram of the Cluster RCT) Ethical and access approval will be obtained from the Ethics Review Committee of The University and study venues, respectively. Potential participants will be referred to the research team by the collaborators. An RA will screen all potential participants for their eligibility to participate in this study. Written informed consent will then be obtained from all of the participants, to whom all aspects of the study will be explained and questions answered. They will then be interviewed to obtain their health-socio-demographic data, and baseline assessment. After that, the twelve community centres will be randomized to either the control, EXER, or COBM group. Participants from each centre will be placed into their centre's corresponding group to avoid 'contamination' effects across participants. At the mid-term programme, 1 week, 6 months, and 12 months post-intervention, an independent assessor who is blinded to the group allocations will assess the participants' outcomes, which will be compared with the baseline assessment. Focus group interviews will be conducted by the trained RA after the first post-test 1 (one-week post-intervention). Purposive samples of 30 participants from the COMB group will be selected to take part in one interview (4-6 per group). They will be asked to comment on their experiences and (dis)satisfaction regarding the programme, perceptions of its positive/negative aspects, concerns and difficulties in participating and adhering to the programme, and ways of improving the intervention. A semi-structured interview guide will be developed for these interviews, which will be conducted in Cantonese, and all interviews will be audio-recorded for content analysis. Examples of interview questions include: "What are your opinions and comments on your participation in the programme?" and "What are your changes and / or difficulties in adherence to the exercise regimen during and after the 16-week programme?"

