SPSS version 23.0 will be used to analyse the data. An intention-to-treat analysis will be adopted. Descriptive statistics will be generated for the demographic data. Normality assumptions for the variables will be checked. The baseline characteristics of the participants in the three groups will be compared using ANOVA for the continuous variables, a chi-square test for the categorical variables, and the Kruskal-Wallis test for the ordinal variables. Mixed-effects modelling will be used to measure changes in the outcome assessments across the mid-term programme (at week 8) and the three post-tests (1 week, 6 months, and 12 months after the intervention) among the three groups, followed by the Helmert contrasts test (if any results are found to be significant)(60). Another mixed-effects modelling approach will be used to measure the participants' attendance rate in the weekly exercise sessions and their adherence to the home exercise during the programme and the follow-up period between the EXER and the COMB groups. Any pre-test outcome scores, demographic information, data on health conditions, comorbidity index, health service utilization, dosages of exercise recommended by the physiotherapist, and participation in other exercise programmes during the study period, indicating significant differences between groups, will be treated as co-variates as needed. Multiple imputations will be adopted to manage missing data. A p-value of < 0.05 will be considered statistically significant. Content analysis will be used to analyse the interview data⁶¹. All audio-taped interviews will be transcribed into Chinese by the RA and the transcriptions will be checked for accuracy by the PI using QSR NVivo 11. The revised transcripts will be coded independently by two (Chinese-speaking) Co-Is. The research team will then discuss the identified codes and come to an agreement on them, grouping them into main (sub)categories with the support of verbatim data. The (sub)categories will then be condensed and/or re-organized when deemed necessary. The research team will examine them for consistency, reach a consensus about their meaning and structure, and devise a list of finalized categories. A set of (sub)categories with supporting verbatim data will finally be generated to identify the major strengths and limitations of the combined intervention to come up with improvements for its future use.

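### The covariate rule lets health service use and exercise variables measured after randomisation into the between-arm models, so an adjusted fatigue result may not estimate the total effect of assignment

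*Protocol*

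**What the plan says.** The Socio-demographic data paragraph of the protocol's Instruments and Measures section defines service use as covering two periods: "in the past 12 months and during the study period, such as the number, duration, and causes of hospital admissions". It adds that these data "causes of hospital admissions and scheduled/non-scheduled clinical visits, will be collected during each measurement time point and will be treated as a co-variate if needed". The measurement points are T0 (baseline), T1 (week 8), T2 (one week after the programme), and T3 and T4 (6 and 12 months after it).

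The SAP gives a list of candidate covariates. It opens with pre-test outcome scores, demographics and health conditions and goes on to "comorbidity index, health service utilization, dosages of exercise recommended by the physiotherapist". It ends with "participation in other exercise programmes during the study period, indicating significant differences between groups, will be treated as co-variates as needed".

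The Procedures section places allocation after consent and baseline assessment: "After that, the twelve community centres will be randomized to either the control, EXER, or COBM group". The SAP also states: "An intention-to-treat analysis will be adopted".

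**The concern.** Service use recorded at T1-T4 for the study period is observed after randomisation, so the intervention may change it. It could do so through fatigue: the protocol's background cites longitudinal work in which older people with general fatigue use more home-help and hospital services. Exercise could also change it directly, by preventing or provoking admissions or visits.

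For a baseline variable, a difference between randomised arms reflects chance. For a variable measured after randomisation, the difference may be an effect of the intervention, and here that difference is what triggers adjustment. The adjusted model then compares arms as if service use had been equal, which is a different question from the effect of being assigned to EXER or COMB.

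The direction is not fixed. If exercise raised admissions and admitted people were more fatigued, adjustment would take that harm out of the fatigue result and overstate the benefit. If exercise lowered admissions, adjustment would understate the benefit.

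**Working it through.** **1. Does the rule reach post-randomisation values?** One could read pre-test at the head of the SAP list as governing every item. Two things tell against that. The protocol expressly includes the study period in the service-use variable that it makes a candidate covariate. The SAP list also contains items that cannot be baseline values: exercise dosage is first set at week 4 (Exercise intervention section), and the last item is explicitly on-study. Dosage is a particular problem in a three-arm model, because controls attend health talks only and have none. Neither document names an unadjusted or baseline-only model as primary.

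**2. Inputs for size.** From the sample size section, the pilot changes were -0.58 (control), -5.16 (EXER) and -2.66 (COMB), with effect sizes 0.51 and 0.23.

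- EXER benefit: 5.16 - 0.58 = 4.58 points; implied SD 4.58/0.51 = 8.98.
- COMB benefit: 2.66 - 0.58 = 2.08 points; implied SD 2.08/0.23 = 9.04.
- An SD of 9.0 is used below, with 95 per arm, four centres per arm and ICC 0.01, as planned.

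The documents give no correlation between service use and fatigue, no admission risks and no effect of an admission on fatigue. Those values are assumed.

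**3. Use is only a consequence of fatigue.** Let r be the within-arm correlation of use with fatigue. The adjusted effect is the total effect × (1 - r²).

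- r = 0.2: 1 - 0.04 = 0.96, so 96% is kept.
- r = 0.4: 1 - 0.16 = 0.84, so 84% is kept.

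On this path the arm difference in use is r × effect size. At r = 0.4 that is 0.4 × 0.23 = 0.09 SD for COMB and 0.4 × 0.51 = 0.20 SD for EXER. As a guide to the trigger, take a three-group F test at 5% with one exercise arm, or both equally, differing from control by d. Then F = n d²/3, and d must reach √(3 × 3.028/95) = 0.31 SD (clustering ignored). The trigger would therefore usually not fire on this path.

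**4. Exercise changes use directly.** Assume 20% of controls and 30% of each exercise arm are admitted, and that an admission adds 4.5 fatigue points. This implies r of about 4.5 × √(0.25 × 0.75)/9.0 = 0.22.

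- Always adjusted: -2.08 - 0.10 × 4.5 = -2.53, which is 0.45/2.08 = 22% too large.
- Reverse case (30% falling to 20%), always adjusted: -2.08 + 0.45 = -1.63, 22% too small.
- Adjusted only when admissions differ significantly, by simulation: the trigger fires in about 36% of trials. The mean COMB effect is -2.30 (0.22/2.08 = 11% too large) or, in the reverse case, -1.81 (0.27/2.08 = 13% too small).

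**5. The intervention does not affect use.** In simulation with equal admission risks, the mean COMB effect is the same with and without adjustment. No bias arises.

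**The case against.** The strongest reply is that nothing here is certain to happen. Both documents leave adjustment to be made as needed. The only comparison of participant characteristics that the SAP describes is at baseline, and it specifies no test of T1-T4 service use. The covariate sentence directly follows the EXER-versus-COMB model for attendance and home-exercise adherence, and dosage fits that two-arm model better than the three-arm fatigue model. All of this stands. A reader might infer that the plan commits to adjusting the primary analysis for on-study service use; the text permits it but does not require it. The list nevertheless opens with pre-test outcome scores, which points to the outcome models, and the protocol's statement on service use is not confined to adherence. Discretion used after the data are seen is not a safeguard.

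A reader might also take 22% as the expected error. That figure supposes adjustment in every trial, whereas the stated rule adjusts only on a significant difference, which roughly halves it. Nor is the gap between the two estimates in triggered trials a measure of bias. In the 20%-versus-30% scenario the unadjusted mean in those trials is about -1.8 and the adjusted mean about -2.5, against a true -2.08. Part of the movement is therefore recovery from chance imbalance. The one link the documents support, from fatigue to later use, gives the smaller attenuation of step 3. The protocol also reports no adverse effects from these exercises in the pilot.

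Finally, a reader might infer a breach of intention-to-treat. Analysing participants as randomised is compatible with covariate adjustment. The problem is which effect the adjusted model estimates.

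**Conclusion.** Wrong as written. The covariate rule permits adjustment for service use, exercise dosage and other exercise participation arising after randomisation. It is triggered by a significant arm difference, with no baseline limit and no protected primary model. If these variables enter the fatigue model, the result is no longer the total effect of assignment.

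The documents do not determine the size. It runs from no bias (the intervention does not affect use), through 4-16% attenuation when the adjustment is made (use is only a consequence of fatigue, assumed r = 0.2 to 0.4), to about 11-13% of the COMB effect in either direction under the trigger rule (assumed admission risks of 20% and 30%, 4.5 points per admission). These are illustrations for a linear model at one visit; a repeated-measures model would differ somewhat. Adjusting for service use in the 12 months before baseline is sound and is not in question.

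**What to change.** In the protocol's Socio-demographic data paragraph and in the SAP, limit covariates in the between-arm outcome models to values measured at or before T0. For service use, that is the figure for the preceding 12 months collected at T0. State that T1-T4 service use, physiotherapist-recommended dosage and on-study participation in other exercise programmes will not enter those models. T1-T4 service use can be reported by arm descriptively if wanted.

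The cost is a change of wording in two places, with no new data, visits or staff. The one thing given up is any precision that T1-T4 service use might have added.

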Aim: The aims of this study are to investigate the effects of an individualized exercise programme with and without BCE strategies for community-dwelling frail older people with general fatigue, so as to reduce their fatigue and improve their physical endurance, exercise self-efficacy, and habitual physical activity, while reducing their symptoms of frailty.

Design: A single-blinded three-arm cluster-RCT is proposed to examine the effect of a 16-week individualized exercise programme with or without BCE strategies for frail older people with general fatigue. To explore the way in which the combined intervention will be implemented (42), a focus group with 30 COMB participants (4-6 per group) will be interviewed by a trained research assistant (RA) to identify the strengths, limitations, and therapeutic components of the combined intervention from their perspectives.

Subjects and Settings: Eligibility criteria for district community health centres are those that are funded by the Hong Kong (HK) government and under the supervision of the Social and Welfare Department of HK, and thus that meet a specific set of standard regulations and criteria on environment and practices. All twelve community centres, which provide similar types of community care and social support services for community dwelling older people, have been invited by a convenience method to work as collaborators in this study. The target population of this study are community-dwelling frail older people with general fatigue with a nonspecific cause who will be recruited through the community centres.

Sample size estimation, recruitment procedures, random allocation, and allocation concealment:

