The Inclusion Criteria are: 1) community-dwelling older people aged > 70 years; 2) able to communicate in Cantonese to ensure that they understand our instructions; 3) able to walk with or without an assistive device and able to complete the Time Up and Go (TUG) test with no specific cutoff point to ensure that their mobility and balance is good enough to join the exercise training; and 4) in a frail state with exhaustion as determined using the Fried Frailty Index (FFI)(7), including: i) an unintentional loss of 10% of body weight in the past year; ii) exhaustion: by answering 'Yes' to either 'I felt that everything I did was an effort', or 'I could not get going in the last week'; iii) a slow walk time: with an average walking speed in the lowest quintile stratified by median body height; iv) reduced grip strength: with maximal grip strength in the lowest quintile stratified by body mass index quartile; and v) the Physical Activity Scale for the Elderly-Chinese (PASE-C) score in the lowest quintile (i.e., < 30 for men and < 27.7 for women). The presence of > 3 items indicates frailty, and one criterion indicates that they suffer from exhaustion.

Sample selection for the focus group: Purposive samples of 30 participants (31.5%) from the COMB group will be selected to join in one interview (if needed, a second interview will be organized for follow-up questions and clarifications). To obtain a wide variety of opinions, six focus groups interviews (4-6 participants per group) will be conducted with 10 participants who had a significant positive reduction in their fatigue scores of > 5 out 20 total score, 10 with a minimal reduction in their fatigue scores of between 1-5, and 10 with no or negative changes on their fatigue score between the baseline and post-test 1 measurement.

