Exercise Self-efficacy: The participants' self-confidence in their ability to exercise in a variety of circumstances (e.g., when feeling tired) will be assessed using the 9-item Chinese Self-Efficacy for Exercise scale (CSEE) (54, 46). The CSEE was validated on 192 Chinese older people. Discriminant validity was shown by the CSEE total score, which significantly differentiated between individuals with or without regular exercise. The Cronbach's α was 0.75, which showed an acceptable level of internal consistency.

Frailty status: This will be assessed based on the FFI mentioned in the sample inclusion criteria (7).

Physical activity level will be assessed using the 10-item PASE-C⁽⁵⁵⁾ to measure self-reported occupational, household, and leisure activities for the last week. Its total score is calculated by multiplying the amount of time spent in each activity (hours / week) by the weight of the pre-set item. PASE-C has been shown across different studies to be a reliable and valid instrument (56, 57).

Depressive Mood: A 15-item C-GDS⁴⁵ will be used on all participants to measure the exhibition of depressive symptoms. The scores '0 to 4', '5 to 9', and '10 to 15' indicate 'normal', 'mild', and 'moderate to severe' depressive mood, respectively. The C-GDS is commonly used in both clinical and research settings, and has shown good reliability and validity^{45, 58}.

Formative or Process Evaluation is aimed at exploring the COMB group participants' perceptions of the strengths and limitations of the intervention. The data will provide valuable insights for the research team to realize / identify the positive components of the combined intervention and the barriers and difficulties faced by the participants in attending/adhering to the intervention.

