Appendix V: The CONSORT diagram of the cluster randomized controlled trial

*Baseline & Outcome Assessments: Fatigue, Physical Endurance, Exercise Self-efficacy Fried Frailty Index, Habitual Physical Activity, Depressive Mood, Exercise Adherence (only for the EXER & COMB groups);

[^]HAPA: Health Action Process Approach

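### The frailty outcome is defined only as frail or not frail in a trial that admits only frail people; prespecifying the number of criteria met (0–5) would be more sensitive and costs one sentence

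*Protocol*

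**What the plan says.** - **Outcome.** Protocol, Secondary outcome measurements: "Frailty status: This will be assessed based on the FFI mentioned in the sample inclusion criteria".
- **Scoring rule and entry condition.** Protocol, The Inclusion Criteria: participants must be "in a frail state with exhaustion as determined using the Fried Frailty Index". Five criteria are listed, followed by the only scoring rule: "The presence of > 3 items indicates frailty, and one criterion indicates that they suffer from exhaustion". The printed sign may stand for three or more; the point does not depend on which.
- **Aim.** Protocol, Aim: frailty is the last of five targets, worded as "while reducing their symptoms of frailty".
- **Timing.** Protocol, Instruments and Measures: outcomes at T1–T4 are to be compared with T0. Appendix V lists "Fried Frailty Index, Habitual Physical Activity, Depressive Mood" among the baseline and outcome assessments, without a scale.
- **Analysis.** SAP: "Mixed-effects modelling will be used to measure changes in the outcome assessments across the mid-term programme (at week 8) and the three post-tests". It gives no scale, link or distribution for frailty. Pre-test scores become covariates, as needed, when they differ significantly between groups.

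**The concern.** For PASE-C, the depression scale and the comorbidity index, the protocol says how the score is formed or banded. For frailty it gives only a threshold, and that threshold is also an eligibility condition. A variable used to select everyone on one value cannot show baseline differences. After baseline it registers only threshold crossings: someone who goes from five criteria to four is still frail whether the cut-off is three or four.

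The aim is graded, and the items needed for a graded measure are already collected. At stake are a real reduction in frailty criteria being missed, and a choice between status and count left open until after the data are seen.

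**Working it through.** **No figure to reproduce.** The documents state no power, rate or effect for frailty. The sample size (76 per group, 95 after attrition) is for fatigue.

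**Step 1: baseline.** From the entry rule, P(frail at T0) = 1, so the variance of status is 1 × (1 − 1) = 0 under either reading of the threshold. The count can still vary over 3–5 (4–5 if the printed sign is literal). With an assumed 60/30/10% at 3/4/5 criteria, the mean is 3.5 and the variance is (9 × 0.6 + 16 × 0.3 + 25 × 0.1) − 3.5² = 12.70 − 12.25 = 0.45. The SAP's covariate rule can therefore never be triggered by baseline status, but could be by the baseline count.

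**Step 2: information at follow-up, closed form.** Let p be the share still frail (three or more criteria) and p_k the share with k criteria. Under proportional odds, the information from status is p(1 − p), and from the six-level count (1 − Σp_k³)/3. The loss is 1 minus the ratio. All distributions below are assumptions.

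| Assumed % with 0/1/2/3/4/5 criteria | Still frail | p(1 − p) | (1 − Σp_k³)/3 | Loss |
|---|---|---|---|---|
| 8/20/32/27/10/3 | 40% | 0.240 | 0.313 | 23% |
| 5/15/30/30/15/5 | 50% | 0.250 | 0.313 | 20% |
| 3/12/25/35/18/7 | 60% | 0.240 | 0.311 | 23% |
| 2/8/20/50/15/5 | 70% | 0.210 | 0.288 | 27% |
| 3/7/20/35/25/10 | 70% | 0.210 | 0.311 | 32% |
| 1/5/14/45/25/10 | 80% | 0.160 | 0.296 | 46% |
| 0/2/8/50/30/10 | 90% | 0.090 | 0.282 | 68% |
| 0/5/45/45/5/0 | 50% | 0.250 | 0.273 | 8% |
| 0/0/40/45/15/0 | 60% | 0.240 | 0.281 | 14% |

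The loss is smallest when nearly everyone sits next to the threshold and largest when nearly everyone stays frail.

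**Step 3: cross-check.** Cutting a normal variable keeps φ(z)²/[p(1 − p)] of its information. The loss is 36% at p = 0.5, 42% at 0.7, 51% at 0.8 and 66% at 0.9.

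**Step 4: simulation with selection at entry.** Five latent-normal criteria (correlation 0.2–0.4, retest correlation 0.5–0.85), entry at three or more including exhaustion, and a treatment shift of 0.3–0.5 latent SD. Efficiency is the squared standardised difference for status divided by that for the count. Across three sets of scenarios, status kept 60–77%, 52–77% and 56–77%, a loss of 23% to between 40% and 48%; I summarise this as about 25–45%. With the printed sign taken literally, status kept about 32–73%, a loss of 27–68%. The count was more efficient in every scenario. The assumed criterion prevalences are not tabulated here, so Step 2 is the part a reader can repeat by hand.

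**Step 5: baseline adjustment.** With correlation ρ between T0 and follow-up counts, adjustment multiplies the residual variance by 1 − ρ²: 0.96 at ρ = 0.2, 0.91 at 0.3, 0.75 at 0.5. Constant status gets none of this. In the simulations, status kept 51–70% of the efficiency of the baseline-adjusted count.

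**The case against.** The strongest reply is that nothing says frailty will be analysed as yes/no. The word status and the single threshold suggest it, but the SAP is silent, Appendix V names only the index, and the threshold itself counts items. A reader might infer that the plan has committed to a binary analysis. The documents do not support that. What stands is that the only definition given is a status, and no 0–5 score is defined anywhere.

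A reader might also infer that the model must fail because T0 has no variation. That would follow only if T0 were a response in a logistic model. The SAP lists week 8 and the three post-tests as the modelled times and specifies no such model. A constant T0 does not bias a comparison of arms at T1–T4.

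Nor is T0 certain to be constant. Procedures places eligibility screening before consent and the baseline assessment after it, and Appendix V includes the index at baseline. If it is repeated there, a few people could fall below the threshold. This objection stands, so the statement about T0 is conditional.

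Finally, grip strength, gait speed and PASE-C, which underlie three of the five criteria, are outcomes in their own right, and fatigue is primary. Much improvement that leaves status unchanged would be visible there. That limits the harm, but none of these measures is the frailty outcome named in the aim. Reversal of frailty is also easier to interpret than a count, which is a reason to keep reporting it.

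**Conclusion.** The point holds as a cheap improvement to a secondary outcome. Frailty is defined only as a status that every participant has at entry, and its scale and model are unspecified. If it is analysed as defined, and the screening assessment serves as T0, it is constant at baseline, cannot support baseline adjustment and misses change that does not cross the threshold. Between-arm comparisons on status after baseline remain valid.

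The size is not fixed by the documents. Relative to the count, the loss is about 25–45% in the latent-variable scenarios with frailty at three or more criteria, and roughly 8–68% over the wider assumed distributions. Leaving clustering aside, 25–45% is like analysing 57 to 42 participants instead of 76 per group (76 × 0.75 = 57; 76 × 0.55 = 41.8). A single narrow figure, such as a quarter to two-fifths, would be tempting but holds only for particular assumed distributions. The direction was the same in every case examined.

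**What to change.** In the protocol's frailty outcome entry and in the SAP, write:

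> The frailty outcome is the number of FFI criteria met (0–5) at each visit, analysed in an ordinal mixed-effects model (linear as a sensitivity analysis) with a centre effect and the T0 number as covariate. The proportion no longer frail is reported alongside as a supportive outcome.

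Also state whether T0 is the screening assessment or a repeat at baseline.

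The cost is one sentence in each document. Scoring the index already requires the five items, so no extra data or visits are needed. The small downside is that a count is less directly interpretable than reversal of frailty, which is why the latter stays in the report.
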